2.2. Background

AD, often known as eczema, is a chronic, inflammatory skin disorder characterized by flaky skin lesions, intense pruritus, and a general deterioration in quality of life (QoL). AD flares occur at variable and unpredictable intervals. Patients with moderate AD may experience approximately 8 flares per year, each lasting approximately 14 days.³

Over the past 50 years, AD has become more prevalent, especially in industrialized, temperate countries such as the US.^{4, 5} AD is one of the most common, chronic, relapsing childhood dermatoses, impacting 15-30% of all children in the US and many have disease that persists into adulthood. Earlier reports indicated that, in up to 70% of cases, the disease greatly improved or resolved by late childhood, however more recent findings suggest that disease activity remains manifest for a prolonged period of time. Based on a total of

7157 patients enrolled in the Pediatric Eczema Elective Registry study, comprising a total of 22,550 person-years, it was concluded that symptoms associated with AD seem to persist well into the second decade of life and likely longer.⁶ The majority of studies conducted across multiple age groups suggest a continued decrease in prevalence with older age.⁷ Adult-onset AD does also occur, though it is less common. The prevalence of AD in adults is estimated to be 10%.⁸

Other treatment options for mild-to-moderate AD include regular use of emollients, topical corticosteroids (TCSs) of low-to-moderate potency, and topical calcineurin inhibitors (TCIs) (eg, pimecrolimus, tacrolimus) as a second line treatment. TCSs and TCIs have limitations for long term use due to safety concerns of TCS (striae rubrae, skin atrophy, telangiectasia, skin burning, erythema, and acneiform or rosacea-like eruptions) and TCI (inhibition of immune surveillance in the skin or systemically and warnings regarding potential for malignancies) adverse effects.^{9, 10} Additional treatments generally reserved for more severe AD include phototherapy (eg, ultraviolet (UV)-A light with or without psoralen, UV-B light narrowband or broadband) and systemic agents (eg, corticosteroids, cyclosporine, recombinant interferon- γ , mycophenolate mofetil, methotrexate, azathioprine, intravenous immunoglobulin and dupilumab).¹¹ Of the currently available therapies, none offers a long-term maintenance solution without long-term use safety concerns for mild-to-moderate AD.^{12, 13}

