3. OBJECTIVES, ESTIMANDS AND ENDPOINTS

Objectives	Endpoints
Primary	

Efficacy: To evaluate the long-term efficacy of crisaborole ointment, 2%, QD for maintenance therapy and flare reduction in pediatric and adult participants ≥ 3 months of age with mild-to-moderate AD who responded to crisaborole ointment, 2%, BID treatment.	
Flare-free maintenance until onset of first flare during the 52-week double-blind period

Safety: To evaluate the safety and local tolerability of crisaborole ointment, 2%, QD for maintenance therapy and flare reduction in pediatric and adult participants ≥ 3 months of age with mild-to-moderate AD	
Incidence of treatment emergent adverse events
Secondary	

To evaluate other long-term efficacy parameters for maintenance therapy and flare reduction of crisaborole ointment, 2%, QD in pediatric and adult participants ≥ 3 months of age	Key secondary endpoints during the 52-week double-blind period: 
Number of flare-free daysNumber of flares

with mild-to-moderate AD who responded to crisaborole ointment, 2%, BID treatment
	
 • Pruritus response maintenance until onset of first flare 
Other secondary endpoints during the 52-week double-blind period:
 
 • $\geq 50\%$ reduction in Eczema Area and Severity Index (EASI)50 response maintenance • Maintenance of Dermatology Quality of Life Assessments • Maintenance of Patient Oriented Eczema Measure (POEM) 
The following will be assessed during flare treatment period:
 
 • Severity of flare on Investigator’s Static Global Assessment (ISGA) and EASI • Duration of flare episode

Additional Secondary
	

 • To evaluate the long-term efficacy of crisaborole ointment, 2%, QD for maintenance therapy and flare reduction in participants ≥ 3 months of age with mild-to-moderate AD 	
The following will be assessed as change from baseline of each respective treatment period (run-in, double-blind, and flare treatment):
 
 • EASI scores • ISGA scores • Treatable AD %BSA • Most commonly affected AD %BSA

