During the open-label run-in period, a responder is defined as a participant who achieves both ISGA success (achieving a score of clear [0] or almost clear [1] with a ≥ 2 grade improvement from the run-in baseline) and at least 50% improvement from the run-in baseline in Eczema Area Severity Index (EASI) score (EASI50).

An end of study (EOS) safety follow-up by phone is required for participants who discontinue from the study at any study period (run-in, maintenance, or flare treatment), 4 weeks after the last study treatment.

Flare Treatment Period

When flares occur during the maintenance period, the participants assigned to either QD treatment arm will be switched to receive flare rescue treatment with crisaborole BID in an open-label setting until resumption of double-blind maintenance treatment. The flare treatment is for up to a maximum of 3 treatment courses each lasting 4 weeks (maximum of 12 weeks).

Flare definition: ISGA ≥ 2

Resolution of flare: ISGA clear (0) or almost clear (1)

During treatment of flares, participants will be assessed every 4 weeks for the following outcomes:

- If ISGA of clear (0) or almost clear (1) is achieved at the end of any of the 4-week treatment courses with crisaborole BID, the participant will resume treatment with their assigned double-blind maintenance therapy.
- If ISGA of clear (0) or almost clear (1) is NOT achieved at the end of 12 weeks of treatment with crisaborole BID, the participant will be discontinued from the study.

For flare treatments that cannot be completed by Week 52 or flares that begin at Week 52, then a maximum of one treatment course (4 weeks) is allowed. Any flare occurring after Week 52 will not be treated for flare treatment by protocol, and the participants should discontinue from the study. EOS follow-up is required in both situations.

The total duration of participation in the study, CCI [REDACTED] including up to 4 weeks for screening, run-in period of up to 8 weeks, 52-week double-blind maintenance period, and follow up period 4 weeks after treatment completion.

See Schema for overall study design ([Section 1.2](#)).

See Schedule of Activities ([SoA](#)) and details of study assessments in [Section 8](#).

CCI

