4.2. Scientific Rationale for Study Design

This study will specifically evaluate if the crisaborole ointment, 2%, QD regimen is safe and efficacious for maintenance therapy and flare reduction during long-term treatment for 52 weeks. The primary and key secondary endpoints are based on the comparison of flare events between crisaborole and vehicle treatments.

The rationale for a QD regimen of crisaborole ointment, 2%, as a maintenance and flare reduction therapy is supported by the efficacy observed in a Phase 2 study (AN2728-AD-204). In Study AN27278-AD-204, crisaborole QD demonstrated that the efficacy onset of response was slower after 1, 2, and 3 weeks of treatment and did not show the same magnitude of AD signs and symptom improvement as BID at the end of 4 weeks of treatment. It was therefore considered that the BID regimen was more suitable for acute treatment of mild-to-moderate AD than the QD regimen. If a flare occurs during the double-blind maintenance period, then BID crisaborole will be provided as a rescue therapy for each flare episode. In the long-term open-label study (AN2728-AD-303) the median time to regain an ISGA score of clear or almost clear after AD relapse following no crisaborole treatment was 84 days. In this study each episode of flare will be treated with crisaborole BID for up to 12 weeks to ensure opportunity for participants to regain the treatment response status before resuming blinded QD maintenance treatment.

The long-term safety of crisaborole ointment, 2%, BID was demonstrated in an open-label extension study (AN2728-AD-303) where participants were treated with on-treatment and off-treatment cycles (corresponding to relapsing-remitting status of AD) for up to 52 weeks. In this study 7 and 8 participants received continuous crisaborole treatment for the entire 48 and 52 weeks, respectively. In this long-term study, no new clinically important safety signal was identified that had not already been identified in the short-term pivotal Phase 3 studies AN2728-AD-301 and AN2728-AD-302. It is therefore considered suitable to evaluate the long-term safety for 52 weeks in this study with crisaborole ointment, 2%, QD.

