		
flare-free days and number of flares as primary analysis
 
 • Treat duration of per flare period and duration of per QD period as continuous endpoints, not as time-to-event • Additional summary for overall DB period for efficacy/PRO endpoints • LOCF data will be used for OL period efficacy summary. • Added additional age subgroup analyses for primary and key secondary efficacy endpoints, evaluation and disposition groups, demographic and baseline characteristics, AE data 	
discontinuation into consideration
 
 • May have too many censor data • Provide efficacy/PRO summary for overall DB period • Based on study design (ie, responders at any time during OL period will be randomized into the DB period) • Per Article 46 requirement
4 20Jan2022	Amendment 1 19May2020	
 • Summary of vital signs (including height and weight) and physical exam was removed • Added safety population for OL 	
 • Team decision • For convenience and consistency among safety tables

		
period and overall study.
 
 Removed subgroup analysis by age groups 3 - <24 months, 2 - <12 years, 12 - <18 years, and ≥ 18 years Removed subgroup analysis for key secondary endpoint maintenance of pruritus response. Removed sensitivity analysis for number of flare-free days and number of flares (annualized data) Prohibited treatment use was removed from intercurrent events 	
 Article 46 no longer apply There are already 5 subgroups for maintenance of pruritus response. Sample size will be too small and may not get robust results by further subgroup analysis. Observed data are more appropriate. Difficult to identify prohibited medication specifically used for AD.
--	--	---	--

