6.3.4.3. Duration of Flare Periods

- Analysis Population: Evaluable-DB.
- Method: Descriptive summary for continuous endpoint. The average duration of flare periods (sum of durations/number of flares) will be calculated for each participant, then summarize the average duration.
- Reporting results: The number of participants, mean, standard deviation, median, minimum, maximum by DB treatment assignment and overall.

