6.4.5. Duration of Flare-free periods

- Analysis Population: Evaluable-DB.
- Method: Descriptive summary for continuous endpoint. The average duration of flare-free periods (sum of durations/number of flare-frees) will be calculated for each participant, then summarize the average duration.
- Reporting results: The number of participants, mean, standard deviation, median, minimum, maximum.

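### SAP 6.3.4.3 averages resolved and unresolved flares together on a 4-week grid, so the reported flare duration can be wrong in either direction

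*SAP*

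**What the plan says.** Protocol section 3 lists "Duration of flare episode" as a secondary endpoint for the flare treatment period. SAP 6.3.4.3 analyses it in Evaluable-DB as a continuous variable: "The average duration of flare periods (sum of durations/number of flares) will be calculated for each participant, then summarize the average duration". The output is n, mean, SD, median, minimum and maximum, by assigned arm and overall. The section gives no censoring rule, no count of unresolved flares and no definition of when a flare period ends.

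The SAP version history (version 3) records the choice as deliberate: "Treat duration of per flare period and duration of per QD period as continuous endpoints, not as time-to-event". The reason given is "May have too many censor data".

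Protocol 4.1 lets a flare period end in three ways:
- ISGA 0 or 1 is seen at an assessment, held every 4 weeks.
- ISGA 0 or 1 has not been reached after 12 weeks, and the participant is discontinued.
- Treatment cannot be completed by Week 52, or the flare begins at Week 52: "then a maximum of one treatment course (4 weeks) is allowed".

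SAP 6.4.5 handles the opposite state in the same way: "The average duration of flare-free periods (sum of durations/number of flare-frees) will be calculated for each participant".

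**The concern.** Only the first of the three endings is resolution, but the average treats all three as completed durations. A flare that led to withdrawal at 12 weeks counts as about 84 days, the same as one that cleared at the third assessment. A failing flare cut off near Week 52 after one course counts the same as one that cleared in a single course. Expecting heavy censoring is a reason to keep a method that handles it; a plain mean only hides it.

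There is a second distortion. Because resolution is seen only every 4 weeks, a single flare can be recorded only as about 28, 56 or 84 days, give or take the visit window. Quick resolutions are rounded up and slow ones are cut off. A reader of the study report would take the mean as how long a flare lasts on twice-daily crisaborole, and it would not be that.

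**Working it through.** **The plan's own figure.** The documents give no planning figure for flare duration. The only related figure is the power in protocol 9.2: 162 events, hazard ratio 0.556, two-sided 0.05. Schoenfeld: z = (√162 / 2) × |ln 0.556| − 1.96 = 6.364 × 0.587 − 1.96 = 1.776, which gives power 0.962. The stated value of about 96% is reproduced (Freedman's form gives 0.953).

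**Inputs.**
- Protocol 9.2: 162 first flares in about 250 participants randomized 1:1, hazard ratio 0.556.
- Protocol 4.1: 52 weeks (364 days), 28-day courses, 84-day cap.
- Median time to resolution: not given for flares as this trial defines and treats them, so a range is used. The low end is protocol 2.2: "Patients with moderate AD may experience approximately 8 flares per year, each lasting approximately 14 days". The high end is protocol 4.2, where the median time to regain clear or almost clear after "relapse following no crisaborole treatment was 84 days".

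**Single flare, closed form.** With exponential resolution and median m, the share unresolved at day t is S(t) = 2^(−t/m).
- Recorded mean = 28 × [1 + S(28) + S(56)].
- True mean = m / ln 2.
- m = 14: 28 × (1 + 0.25 + 0.0625) = 36.8 recorded; 20.2 true.
- m = 84: 28 × (1 + 0.794 + 0.630) = 67.9 recorded; 121.2 true.

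**Whole trial, simulation.** The vehicle first-flare hazard h solves ½(1 − e^(−364h)) + ½(1 − e^(−364 × 0.556h)) = 162/250 = 0.648. This gives h = 0.00386 per day, so 75.4% of vehicle and 54.2% of crisaborole participants flare (mean 64.8%). There were 40,000 simulated participants per arm, with the same resolution rate in both arms and no other dropout. Week 52 was read as: a course under way is completed and no further course starts. Results are vehicle / crisaborole.

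| Median (days) | Unresolved at 12 weeks | Cut at Week 52 | Total unresolved | Planned average (days) | True mean, m / ln 2 (days) |
|---|---|---|---|---|---|
| 14 | 1.2 / 1.3% | 2.2 / 2.3% | 3.4 / 3.6% | 36.3 / 36.1 | 20 |
| 28 | 10.6 / 10.9% | 5.4 / 5.6% | 16.0 / 16.5% | 48.7 / 48.0 | 40 |
| 42 | 21.6 / 21.4% | 6.8 / 7.2% | 28.4 / 28.6% | 56.4 / 55.3 | 61 |
| 56 | 31.2 / 30.2% | 7.5 / 8.5% | 38.7 / 38.7% | 61.4 / 59.8 | 81 |
| 84 | 44.4 / 43.3% | 8.1 / 9.2% | 52.5 / 52.5% | 67.1 / 65.2 | 121 |

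Rounding up dominates at medians of 28 days or less, and cut-off dominates from 42 days. Across a sixfold range of medians the planned average moves only from about 36 to 67 days. At 84 days the median participant average is 84, which is the cap itself.

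**With censoring.** Kaplan-Meier on the same simulated flares, with unresolved ones censored, returns the assumed curve. At an 84-day median the shares unresolved at 28/56/84 days are 0.796/0.630/0.501 on vehicle and 0.788/0.625/0.498 on crisaborole, against 0.794/0.630/0.500 in theory.

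**SAP 6.4.5.** On planning figures 250 − 162 = 88 participants, 88/250 = 35%, have a first flare-free period that never ends in a flare. Each is averaged as complete.

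**No flare.** About 25% of vehicle and 46% of crisaborole participants would have no flare. For them the 6.3.4.3 formula is 0/0, and the SAP does not say that they are left out.

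**The case against.** The strongest reply is that much of this can be seen elsewhere. SAP 6.3.4.1 tabulates ISGA categories in the first flare period at Weeks 0, 4, 8 and 12, by arm and overall, and ISGA 0 or 1 is resolution. SAP 6.6.2 summarises discontinuations. That stands in part: first-flare non-resolution can be partly read from those tables. They do not cover later flares, do not say why a flare period ended, and lose participants as they resolve. They also leave the average unchanged.

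On 6.4.5, the SAP does not claim that each period ended in a flare. Section 6.2.1 openly says that censored flare-free days are truncated, and the primary analysis already gives Kaplan-Meier for the first period. All true, but the mixed average is still planned.

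A reader might infer three stronger things that the documents do not support:
- That more than half of flares will end unresolved. This rests on the 84-day median, from an earlier study and worded so that its application to flares treated twice daily is unclear. The 14-day figure gives about 3.5%, but it describes flares in general and not ISGA-defined ones.
- That the plan always understates duration. With fast resolution it overstates it. A per-course model makes the shortfall look larger, with a mean of 28 / (1 − 0.5^(1/3)) = 136 days at an 84-day median, but that figure carries the same 4-week rounding.
- That the endpoint measures only treatment-course length. Resolved flares do end on a clinical criterion, although it is observed only every 4 weeks.

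**Conclusion.** The point holds. SAP 6.3.4.3 gives a rule, and following it produces a mean that counts failed and cleared flares alike, so this is an unsuitable method and not just missing detail. It is also out of step with SAP 6.1.1 and 6.3.1 to 6.3.3, which right-censor and report the number censored.

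The size is uncertain: about 3% to 53% of flares enter unresolved, with an error from about 16 days too long (14-day median) to about 54-56 days too short (84-day median). These figures assume exponential resolution times, no other dropout and the stated reading of the Week 52 rule. The true means for slow resolution also extrapolate beyond 12 weeks, where the design has no data.

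The endpoint is descriptive, non-key and outside the testing hierarchy. With equal resolution in both arms, the simulated arms differ by less than 2 days. A reader should not conclude that a tested treatment claim is distorted; what is affected is the meaning of the reported duration. The change should be made, but the trial's main conclusion does not depend on it.

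**What to change.** In SAP 6.3.4.3:
- State how the start and end dates of a flare period are taken, and restrict the analysis to participants with at least one flare.
- By assigned arm and overall, for first flares and for all flares, report the number and percent resolved at the end of courses 1, 2 and 3, unresolved at 12 weeks, and cut off by Week 52 or dropout.
- For the first flare, replace the plain average with a discrete-time or interval-censored estimate of time to resolution on the 4-week grid, with unresolved and cut-off flares right-censored. Ordinary Kaplan-Meier on 28/56/84-day values would deal with the censoring but leave the rounding.

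In SAP 6.4.5, refer to the primary Kaplan-Meier analysis for the first flare-free period and drop the average that mixes completed and censored periods.

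The cost is SAP wording and one table, from ISGA data already collected. Protocol 9.4.1.2 leaves other secondary analyses to the SAP, and protocol 9.4 requires an amendment only for major changes to primary or key secondary endpoints. The downside is that a median may not be reached; then only the percent resolved per course is quoted.

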6.4. Additional Secondary Endpoints

Analyses of secondary endpoints for OL period will be based on LOCF data.

Analyses of secondary endpoints for DB period will be based on observed data.

6.4.1. EASI

- OL period:
 - Analysis Population: Evaluable-OL.
 - Method: Descriptive summary for continuous endpoint.
 - Reporting results: The number of participants, mean, standard deviation, median, minimum, maximum for observed value and change from OL baseline by time point.
- DB period, First flare-free period, and First flare period:
 - Analysis Population: Evaluable-DB.
 - Method: Descriptive summary for continuous endpoint.
 - Reporting results: The number of participants, mean, standard deviation, median, minimum, maximum for observed value and change from randomization in the DB period (Flare-free/Flare), the first flare-free period, and first flare period. For the first flare period, the change is the change from the start of first flare period, summary is performed by the time point relative to the start of first flare period (ie, Weeks 0, 4, 8, 12 in the first flare period).

6.4.2. ISGA

- OL period:
 - Analysis Population: Evaluable-OL.
 - Method: Descriptive summary for binary endpoint; Descriptive summary for continuous endpoint.
 - Reporting results:

- ISGA success and ISGA clear/almost: the number and percent (95% CI) by time point.
 - ISGA as a categorical endpoint: the number and percent of participants.
 - ISGA as a continuous endpoint: the number of participants, mean, standard deviation, median, minimum, maximum for observed value and change from OL baseline by time point.
- DB period, First flare-free period, and First flare period:
 - Analysis Population: Evaluable-DB.
 - Method: Descriptive summary for categorical and continuous endpoints.
 - Reporting results:
 - ISGA as a categorical endpoint: the number and percent of participants.
 - ISGA as a continuous endpoint: the number of participants, mean, standard deviation, median, minimum, maximum for observed value and change from randomization in the DB period (Flare-free/Flare), the first flare-free period, and first flare period. For the first flare period, the change is the change from the start of first flare period, summary is performed by the time point relative to the start of first flare period (ie, Weeks 0, 4, 8, 12 in the first flare period).

6.4.3. Treatable AD %BSA

- OL period:
 - Analysis Population: Evaluable-OL.
 - Method: Descriptive summary for continuous endpoint.
 - Reporting results: The number of participants, mean, standard deviation, median, minimum, maximum for observed value and change from OL baseline by time point.
- DB period, First flare-free period, and First flare period:
 - Analysis Population: Evaluable-DB.
 - Method: Descriptive summary for continuous endpoint.
 - Reporting results: The number of participants, mean, standard deviation, median, minimum, maximum for observed value and change from randomization in the DB period (Flare-free/Flare), the first flare-free period, and the first flare period. For the first flare period, the change is the change from the start of first flare period, summary is performed by the time point relative to the start of first flare period (ie, Weeks 0, 4, 8, 12 in the first flare period).

